3.0 BACKGROUND AND RATIONALE

3.1 Current Adjuvant Standards for Gastric Cancer

Gastric adenocarcinoma, also known as stomach cancer, is a global health problem. While surgical resection remains the only curative option for patients who develop this disease, because of its aggressive nature and high recurrence rates, all but the lowest stages of gastric cancer require additional, adjuvant therapy in addition to surgery. Currently, two competing standards exist for the adjuvant management of gastric cancer: peri-operative chemotherapy (based upon the MAGIC study), and postoperative combination chemoradiation therapy (based upon the MacDonald Intergroup study).^{1,2} These two standards were arrived at based upon two separate trials that did not directly compare the two approaches, and thus either approach is considered acceptable. Several modifications to the chemotherapy used in the peri-operative approach have been studied and are now accepted as standard as well.^{3,4,5} Selection oftentimes derives from physician preference and tumor characteristics such as symptoms or nodal stage, and a clear guideline for when to select one adjuvant approach over the other is lacking.

Currently, analysis of patient outcomes from the large, randomized phase III CRITICS trial is ongoing, and will attempt to answer if one approach is clearly favored.⁶ Patients enrolled in the CRITICS trial all received preoperative chemotherapy and standardized surgical resection. Patients were then randomized to receive either chemotherapy or chemoradiation therapies postoperatively. Enrollment is closed for the CRITICS trial; preliminary data suggest that neither arm of postoperative treatment is superior.⁷ These early data support what practitioners have long suspected, which is that no one adjuvant standard is universally superior, but that tumors from different patients and with different characteristics will respond better to different adjuvant approaches.

Unfortunately, knowing which tumors will respond better to which therapy remains unpredictable. Certain clinical features can help clinicians to make a recommendation for their adjuvant approach. For example, patients who have tumors that are symptomatic, such as with bleeding or gastric obstruction, are less likely to tolerate several months of surgical delay while chemotherapy is administered preoperatively, and thus will typically be offered upfront surgery, followed by adjuvant chemoradiation. For most patients, however, the administration of systemic therapy prior to surgery as a part of a perioperative approach is recommended. This approach is favored because of the local control and reduction in tumor that can result prior to surgery, which is thought to lead to better outcomes in the long term.

However, not all patients will experience a response to preoperative chemotherapy. In those patients whose tumors are found at surgery to remain advanced, with nodal involvement, despite preoperative chemotherapy, long-term outcomes have been shown to be poorer than those whose tumors responded well, with the absence of nodal involvement upon dissection.⁸ These data are based upon the retrospective analysis of those patients who were enrolled in the original MAGIC study. Approximately 75% of tumors were found to be in the category of having nodes involved with cancer at resection despite preoperative chemotherapy. Thus, for this majority of patients with gastric cancer who have an inadequate response to preoperative chemotherapy (i.e., who remain node-positive at surgery), an alternative approach to their postoperative adjuvant treatment rather than mere completion of postoperative chemotherapy is apparently necessary.

One reasonable alternative for the management of patients who remain node positive at surgery

could be to incorporate radiation into their postoperative adjuvant treatment. There is some evidence for this approach, coming from the South Korean ARTIST trial.^{9,10} In the ARTIST trial, patients who underwent gastrectomy for stomach cancer randomly received either post-operative chemotherapy or chemoradiation therapy. Although no overall survival benefit was seen overall in the ARTIST study, in subset analysis, node positive patients had a significant improvement in disease-free survival with adjuvant chemoradiotherapy versus adjuvant chemotherapy alone.

3.2 Rationale for Piloting Chemotherapy versus Chemoradiation

Historically, administration of postoperative adjuvant therapy of any type is challenging following gastrectomy. In both the MAGIC and in the MacDonald Intergroup trials, less than 50% of patients were able to complete the postoperative adjuvant therapy recommended.^{1,2} Given improvements in patient selection, surgical techniques, methods for accelerating recovery after surgery, and improved management of chemotherapy toxicity, it is reasonable to expect that many more patients are able to complete these recommended postoperative therapies in current practice. However, this has not been validated. The feasibilities of the individual components of the proposed approach in this protocol are established standards. However, the use of chemoradiation following both pre-operative chemotherapy and surgery as a standard recommendation, based upon an objective surgical finding, is novel. Typically, patients who receive post-operative chemoradiation have received no preoperative therapy. Thus, the administration of chemoradiation to a patient after surgery who received chemotherapy prior to surgery is experimental. Additionally, the treating physicians oftentimes elect to eliminate the radiation if they arbitrarily feel that the patient may not benefit from it. Assuming the rates of node positive disease mirror those observed in the MAGIC protocol's retrospective review⁸, then the majority of patients will receive the recommendation for chemoradiation. When recommended, the administration of postoperative radiation to chemotherapy following preoperative chemotherapy and surgery for this majority of patients with node positive disease may or may not be feasible, depending upon the patients' abilities to tolerate such therapy. If feasible, the ability to study the larger questions of outcomes will be possible; this needs to be known before such a larger study is entertained. Finding that such therapy is not feasible for routine recommendation and administration despite an objective surgical result suggesting it is indicated would necessitate development of a trial of an alternative intervention for the management of these patients who have an anticipated poorer outcome. Therefore, piloting the use of postoperative chemoradiation therapy to determine if this is a feasible recommendation for further exploration of benefit is warranted.

Given the improvements in the ability to administer these therapies, it is reasonable to expect that no more than 30% of patients would be unable to complete all recommended therapy. While the use of chemoradiation for the treatment of patients with node positive disease serves as an intervention arm, inclusion of the roughly 25% of patients who will likely have node negative disease and receive standard post-operative chemotherapy alone is important to confirm similar rates of successful completion of therapy.

3.3 Background on Proposed Correlative Studies

The disparity in tumor responses to preoperative chemotherapy supports biologic heterogeneity of these tumors. Understanding these biologic differences would be invaluable to the future therapeutic direction of their management. These differences are likely complex, existing as baseline genetic characteristics at diagnosis but also as dynamic changes in these characteristics in response to chemotherapy. Identifying these characteristics could allow clinicians to determine which patients' tumors are unlikely to respond to therapy upfront or how to modify ongoing therapy in response to tumor response and evolution as therapy is administered. Knowing that tumor nodal response to preoperative chemotherapy is a surrogate for outcomes in these patients can provide an important comparator for groups of gene expression and evolution.

Recent work into the characterization of gastric adenocarcinoma suggests that four distinct molecular subtypes exist.¹¹ These subtypes are characterized as Epstein-Barr virus positive, microsatellite unstable, genomically stable, and chromosome instable. Determination of the genetic features giving rise to each category is based upon analysis of virgin tumor samples, and thus does not consider variations that arise in response to treatment. Nevertheless, each subtype is characterized by the expression or mutation of specific genes or gene categories that can be profiled through routine analysis. Correlating these gene expressions to clinical nodal responses to chemotherapy could potentially offer insights into the biomarker driven determination of adjuvant treatment selection in gastric cancer. Additionally, monitoring these gene expression levels in response to therapy and making similar correlates could provide valuable information into the adaption of adjuvant therapy to the tumor's response to treatment in real time.

The genes associated with these four proposed subtypes of gastric cancer are by no means exhaustive, however, and the expression or alteration of other genes may yield further predictive and therapeutic information for the adjuvant treatment of these cancers. Casting a wider net is increasingly easy to accomplish, with the advent of genomic profiling of tumors. Particularly in the case of profiles that assess for expression of targetable genes, the ability to assess or monitor for their expression as they relate to chemotherapy response could have important implications for being able to incorporate the therapies into the adjuvant treatment process at critical junctures in the treatment sequence.

4.0 STUDY DESIGN

4.1 This study is a stratified, two-arm, open label, pilot design, for patients who have received the standard three cycles of preoperative chemotherapy and then standard surgical resection.

Patients found to be node-negative at time of surgery will be treated with standard three cycles of standard postoperative chemotherapy, **Arm 1**.

Patients found to be node-positive at time of surgery will receive radiation in addition to chemotherapy, **Arm 2**.

4.2 Treatment interventions

All patients will have received three cycles of preoperative chemotherapy (CAPEOX or FOLFOX, at the treating physician's discretion), followed by standard cancer surgery.

Patients will then be assigned to one of two treatment cohorts for postoperative therapy, based upon nodal involvement by cancer in the surgical specimen.

- 4.2.1 **Arm 1:** Patients who are found to be node negative at surgery will complete an additional three postoperative cycles of chemotherapy. Again, this chemotherapy will be CAPEOX or FOLFOX, at treating physician's discretion. This does not need to be the same regimen as was given pre-operatively, but could be changed to the other regimen, at the treating physician's discretion.
- 4.2.2 **Arm 2:** Patients who are found to be node positive at surgery will instead receive chemoradiation, using single agent fluoropyrimidine (5-fluorouracil or capecitabine) as the chemotherapeutic and receiving 45 Gy of radiation. This does not need to be the same fluoropyrimidine as was given pre-operatively with the oxaliplatin, but could be changed to the other fluoropyrimidine, at the treating physician's discretion.

4.3 Genetic profile correlative studies

- 4.3.1 All patients will have undergone two tumor tissue acquisitions during standard clinical practice. Specimens from these acquisitions must be available:
- Prior to initiation of preoperative chemotherapy, tumor tissue will be obtained from the diagnostic biopsy samples;
 - Tumor tissue will be obtained at the time of surgery.

Both of these samples will be a part of standard of care, thus no additional biopsies beyond this standard will be performed for the study.

A preselected panel of genetic markers will be assessed for expression within each sample, and compared for differences, pre- and post-chemotherapy. These differences will be correlated for any response in tumor, i.e., node positive versus node negative.

5.0 SUBJECT ELIGIBILITY: Patient Initials (L,FM): _____

5.1 Inclusion Criteria:

- 1) Must have pathologically-proven adenocarcinoma of the stomach or gastroesophageal (GE)-junction, stage M0, as established by both imaging and surgical pathologic staging.

Imaging: Clinical stage of M0 will be established by either CT (chest with contrast and abdomen/pelvis with and without contrast), or CT/PET (skull base to mid-thigh). This is standard post-surgery imaging.

Surgery: Surgical pathologic staging must be M0.

- 2) Must have completed 3 cycles of neo-adjuvant chemotherapy. Either CAPEOX or

FOLFOX is allowed. Dose modifications are allowed, but all 3 cycles must have been completed.

- 3) Must have undergone a surgical resection with definitive intent, either by open or laparoscopic resection of the primary gastric or GE junction cancer. Patients must have undergone a total gastrectomy, subtotal gastrectomy, or distal gastrectomy (depending on the location of primary gastric lesion) with at least a modified D2 lymphadenectomy.
- 4) Must be deemed as a good candidate for adjuvant chemotherapy or chemoradiation (to start within 3 months of surgery), in the opinion of the treating investigator. Plan must be to start adjuvant therapy within 90 days of surgery; adjuvant treatment cannot begin more than 90 days after surgery.
- 5) Must have diagnostic biopsy tissue (pre-neoadjuvant chemo) available for genetic testing.
- 6) Must have surgical tissue (post-neoadjuvant chemo) available for genetic testing.
- 7) Must be ≥ 18 years of age.
- 8) Must be able to provide informed consent.
- 9) Must have adequate kidney, liver, and bone marrow function, within 28 days prior to registration, as follows:
 - i. Hemoglobin ≥ 8.0 gm/dL
 - ii. Absolute neutrophil count (ANC) ≥ 1500 cells/mm³
 - iii. Platelet count $\geq 75,000$ /mm³
 - iv. Calculated creatinine clearance of > 60 mL/min/m², calculated as follows:
For males = $\frac{(140 - \text{age [years]}) \times (\text{body weight [kg]})}{(72) \times (\text{serum creatinine [mg/dL]})}$
For females = $0.85 \times$ male value
 - v. Total bilirubin ≤ 1.5 times upper limit of normal (ULN)
 - vi. AST (SGOT) and ALT (SGPT) ≤ 3.0 times the ULN
- 10) Must have life expectancy of greater than 3 months.
- 11) Must have an ECOG performance status 0-2.
- 12) Male or female patients of childbearing potential must be willing to use contraceptive precautions throughout the trial and 3 months following discontinuation of study treatment. Post-menopausal women must be amenorrheic for at least 12 months to

be considered of non-childbearing potential.

5.2 Exclusion Criteria

- 1) Other than the 3 cycles of neoadjuvant chemotherapy and surgery (mentioned above), must not have received other treatment for their gastric cancer.
- 2) Female patients who are pregnant, breast feeding, or of childbearing potential without a negative pregnancy test prior to baseline. Women of childbearing potential must have a negative serum pregnancy test as a part of eligibility, within 28 days of registration.
- 3) Patients unwilling or unable to comply with the protocol, or provide informed consent.
- 4) Patients with clinical evidence of metastatic disease.
- 5) Any medical condition that, in the opinion of the investigator, would exclude the patient from participating in this study and treatment plan.

6.0 CLINICAL AND LABORATORY EVALUATIONS

6.1 Screening / Baseline Evaluation

- 6.1.1 Diagnostic (biopsy) and surgical confirmation of adenocarcinoma of gastric or GE junction origin; samples to be used for genetic profile.
- 6.1.2 A medical history and physical exam (H&P) to include the following information:
 - 6.1.2.1 A signs and symptoms assessment, including history of weight change
 - 6.1.2.2 Complete physical exam, including the following: vital signs, height, weight, and ECOG performance status.
 - 6.1.2.3 Baseline Toxicity Assessment
- 6.1.3 Laboratory studies must be obtained within 28 days (unless noted otherwise) prior to registration, to include the following:
 - 6.1.3.1 Complete blood count (CBC) with differential and platelets.
 - 6.1.3.2 Serum chemistries: liver enzymes (AST, ALT, alkaline phosphatase), blood urea nitrogen (BUN), creatinine, electrolytes (sodium, potassium, chloride, calcium, bicarbonate), total protein, albumin, total bilirubin, and glucose.
 - 6.1.3.3 For women of child bearing potential, a serum β -HCG pregnancy test.

- 6.1.4 Tumor imaging with either CT (chest with contrast and abdomen/pelvis with and without contrast) or CT/PET (skull base to mid-thigh); must be within 42 days of treatment start.
- 6.1.5 Pathologic evaluation of tumor specimen will include standard lymph node evaluation. Nodal disease will be classified into one of two categories:
 - lymph node negative, where no nodes are involved with tumor, or lymph node positive, where one or more nodes are involved with tumor.

6.2 Arm 1: Adjuvant Chemotherapy: Evaluation of patients deemed lymph node negative at time of surgery and treated with postoperative chemotherapy:

- 6.2.1 Within 2 days before Day 1 treatment of each cycle (for either chemo regimen):

- 6.2.1.1 History and physical exam

- 6.2.1.2 Vital signs (blood pressure, respiratory rate, height, weight)

- 6.2.1.3 Complete blood count (CBC) with differential and platelets.

- 6.2.1.4 Serum chemistries: liver enzymes (AST, ALT, alkaline phosphatase), blood urea nitrogen (BUN), creatinine, electrolytes (sodium, potassium, chloride, calcium, bicarbonate), total protein, albumin, total bilirubin, and glucose.

- 6.2.1.5 Adverse Event Assessment

6.3 Arm 2, Adjuvant Chemoradiation: Evaluations for patients deemed lymph node positive at time of surgery and treated with postoperative chemoradiation:

- 6.3.1 While on chemotherapy alone, within 2 days before Day 1 treatment of each cycle:

- 6.3.1.1 History and physical exam

- 6.3.1.2 Vital signs (blood pressure, respiratory rate, height, weight)

- 6.3.1.3 Complete blood count (CBC) with differential and platelets.

- 6.3.1.4 Serum chemistries: liver enzymes (AST, ALT, alkaline phosphatase), blood urea nitrogen (BUN), creatinine, electrolytes (sodium, potassium, chloride, calcium, bicarbonate), total protein, albumin, total bilirubin, and glucose.

- 6.3.1.5 Adverse Event Assessment

6.3.2 While on concurrent chemoradiation (for 5 weeks), once per week:

6.3.2.1 History and physical exam

6.3.2.2 Vital signs (blood pressure, respiratory rate, height, weight)

6.3.2.3 Complete blood count (CBC) with differential and platelets.

6.3.2.4 Serum chemistries: liver enzymes (AST, ALT, alkaline phosphatase), blood urea nitrogen (BUN), creatinine, electrolytes (sodium, potassium, chloride, calcium, bicarbonate), total protein, albumin, total bilirubin, and glucose.

6.3.2.5 Adverse Event Assessment

6.4 Post-Treatment Surveillance (Follow-Up)

6.4.1 After completion of adjuvant chemotherapy, subjects will undergo follow-up, every 3 months, +/- 14 days, for a total of 36 months from the date of surgery.

6.4.1.1 History and physical exam

6.4.1.2 Vital signs (blood pressure, respiratory rate, height, weight)

6.4.1.3 Complete blood count (CBC) with differential and platelets.

6.4.1.4 Serum chemistries: liver enzymes (AST, ALT, alkaline phosphatase), blood urea nitrogen (BUN), creatinine, electrolytes (sodium, potassium, chloride, calcium, bicarbonate), total protein, albumin, total bilirubin, and glucose.

6.4.1.5 Survival Status

6.4.1.6 Recurrence of disease (date of recurrence)

6.4.1.7 Adverse Event Assessment (per Section 13.6.3)

6.4.2 Patients will undergo imaging for residual or recurring tumor with either CT (chest with contrast and abdomen/pelvis with and without contrast) or CT/PET (skull base to mid-thigh). The interval of this imaging can be every 3-6 months, at the discretion of the treating investigator.

7.0 TREATMENT PLAN

Preoperative chemotherapy: Patients will have received 3 cycles of neo-adjuvant chemotherapy (either CAPEOX or FOLFOX) at the treating physician's discretion. Dose modifications are allowed per standard clinic practice.

After the completion of the preoperative therapy, patients without evidence of obvious metastatic disease will undergo a surgical resection with definitive intent, either by open or laparoscopic resection of the primary gastric or GE junction cancer.

After completion of surgery, patients will be reviewed for eligibility. Eligible subjects will be registered to the study and assigned to Arm 1 or Arm 2.

Treatment should start within 3 months of surgery.

All adjuvant treatment regimens (both Arm 1 and Arm 2) are to be administered per standard clinic practices, including infusion duration times, dose modifications, treatment delays, and supportive care.

7.1 Arm 1: Postoperative chemotherapy, for those patients with node negative disease at time of surgery, will consist of three additional cycles of chemotherapy. Subjects can receive either CAPEOX or FOLFOX (regardless of the neo-adjuvant regimen), following the same dosing guidelines and management as below. Changing to the alternative fluoropyrimidine (capecitabine or 5-fluorouracil) from what was used pre-operatively is permissible at the discretion of the treating investigator.

7.1.1 CAPEOX will be dosed on a 21-day cycle:

AGENT	DOSE	ROUTE	DAYS	INTERVAL
Oxaliplatin	130 mg/m ²	IV	Day 1	21-day cycle
Capecitabine	625 mg/m ²	PO (BID)	Days 1-5, 8-12, 15-19	21-day cycle

or

[figure not shown]
AGENT	DOSE	ROUTE	DAYS	INTERVAL
Oxaliplatin	130 mg/m ²	IV	Day 1	21-day cycle
Capecitabine	1000 mg/m ²	PO (BID)	Days 1-14	21-day cycle

7.1.2 FOLFOX will be dosed on a 14-day cycle. Agents are to be given in this order, according to standard clinic practice.

AGENT	DOSE	ROUTE	DAYS	INTERVAL
Oxaliplatin	85 mg/m ²	IV	Day 1	14-day cycle
Leucovorin	400 mg/m ²	IV	Day 1	14-day cycle
5-fluorouracil*	400 mg/m ²	IV bolus	Day 1	14-day cycle
5-fluorouracil*	2400 mg/m ²	Continuous IV infusion	Day 1-3	14-day cycle

* 5-fluorouracil will be dosed as 400 mg/m² through IV bolus, followed by 2400 mg/m² through continuous IV infusion, starting Day 1

7.2 Arm 2: Postoperative chemoradiation, for those patients with node positive disease at time of surgery, will consist of one cycle of chemotherapy, followed by concurrent chemoradiation (5 weeks), and followed by two additional cycles of chemotherapy.

7.2.1 Each cycle of chemotherapy-alone will consist of a single agent fluoropyrimidine, either capecitabine (per section 7.2.1.1) or 5-fluorouracil (per section 7.2.1.2), at the treating physician's discretion.

7.2.1.1 Capecitabine will consist of 750 mg/m², PO BID on days 1-14 of a 28 day cycle.

AGENT	DOSE	ROUTE	DAYS	INTERVAL
Capecitabine	750 mg/m ²	PO (BID)	Days 1-14	28-day cycle

7.2.1.2 5-fluorouracil will be given on days 1 and 15 of a 28 day cycle according to the following:

- Leucovorin will be dosed as 400 mg/m², IV infusion over 60 minutes
- 5-fluorouracil will be dosed as 400 mg/m², IV bolus followed by a 1200 mg/m², IV infusion over 46 hours

AGENT	DOSE	ROUTE	DAYS	INTERVAL
Leucovorin	400 mg/m ²	IV	Day 1	28-day cycle
5-fluorouracil	400 mg/m ²	IV bolus	Day 1	28-day cycle
5-fluorouracil	1200 mg/m ²	Continuous IV infusion	Day 1-3	28-day cycle

7.2.1.3 Criteria for proceeding with treatment and managing side effects will be as in section 7.4 (below).

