7.2.2.2.1 Capecitabine will consist of 750 mg/m², PO BID on days of radiation

AGENT	DOSE	ROUTE	DAYS	INTERVAL
Capecitabine	750 mg/m ²	PO (BID)	Days of Radiation	5-weeks

7.2.2.2.2 5-fluorouracil will be dosed as 200 mg/m²/day, IV continuous infusion on days of radiation

AGENT	DOSE	ROUTE	DAYS	INTERVAL
5-fluorouracil	200 mg/m ²	IV (over 1 day)	Days of radiation	5-weeks

7.2.2.3 Criteria for proceeding with treatment and managing side effects will be as in 5.1.3.

7.3 Chemotherapy after chemoradiation: After finishing chemoradiation (section 7.2.2), subjects will receive two cycles of chemotherapy alone, as in 7.2.1. Changing to the alternative fluoropyrimidine (capecitabine or 5-fluorouracil) from what was used previously is permissible at the discretion of the treating investigator.

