7.4 Chemotherapy side effect management

7.4.1 All patients will receive anti-emetic prophylaxis, IV, on day 1 of IV chemotherapy.

7.4.2 All patients will be prescribed oral anti-emetics as needed (per investigator discretion and standard clinical care).

7.4.3 Patients that develop diarrhea can be managed using as needed loperamide or other anti-diarrheals, at the discretion of the treating physician.

7.4.4 On Day 1 of each cycle (or, up to 2 days before Day 1), patients must meet the following criteria in order to proceed with treatment:

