10.0 STATISTICAL CONSIDERATIONS

The primary objective is to determine the feasibility of patients enrolling and receiving either postoperative chemoradiation or chemotherapy alone, based upon nodal status. Based on our experience, we projected that the eligible patients would receive chemoradiation or chemotherapy alone in 3:1 ratio after surgery. We designed this pilot study on 30 patients who receive chemoradiation and on 10 patients who receive chemotherapy alone based upon nodal status at surgery, for a total of 40 patients. At 50% of complete rate, the confidence intervals will have widths of a most +/- 17% and +/- 26.5% (confidence intervals calculated using Wilson method). For control purposes, no more than 30% of patients with node negative disease should be unable to receive postoperative chemotherapy. In order for postoperative chemoradiation to be a feasible recommendation in patients who have lymph node positive disease at time of surgery after preoperative chemotherapy, a majority of patients must be able to receive this chemoradiation in its entirety.

The primary endpoint is the proportion of patients who complete the recommended therapies as indicated by their surgical nodal status. The primary endpoint will be evaluated when the last patient completes the postoperative chemotherapy or chemoradiation assigned. Descriptive and summary statistics will be computed for demographics and clinical data of all patients enrolled in the study. In each group, complete rates will be summarized with a point estimate and 95% confidence interval (Wilson method). If no more than 30% of patients are unable to complete all protocol therapy, then this will be considered a feasible treatment for these patients.

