CBC + differential + platelets	X	X	X	X	X	X	X	X	X	
CMP: Serum Chemistries (3)	X	X	X	X	X	X	X	X	X	
AE Assessment		X	X	X	X	X	X	X	X	
Pregnancy Test	X									
Tumor for genetic profile (4)	X									
Imaging (5)	X								X	
Chemo, Adjuvant		X	X	X	X	X	X	X	X	
Concurrent XRT			X	X	X	X	X			
XRT Treatment Report (8)							X			
Survival Status, Recurrence									X	

1. Screening procedures must be obtained within 28 days of registration, with the exception of radiographic studies and tumor samples for baseline profiles.
2. Vital signs includes blood pressure, respiratory rate, height, and weight.
3. Serum chemistries to include: liver enzymes (AST, ALT, alkaline phosphatase), blood urea nitrogen (BUN), creatinine, electrolytes (sodium, potassium, chloride, calcium, bicarbonate), total protein, albumin, total bilirubin, glucose.
4. Tumor samples from diagnostic biopsy (before neo-adjuvant chemo) and surgery (after neo-adjuvant chemo) should be obtained (after subject consents to participate).
5. Can be either (1) CT of the chest with contrast and CT of the abdomen/pelvis with and without contrast, or (2) PET/CT from the skull base to mid-thigh. Baseline imaging must be after surgery, and within 42 days of starting adjuvant chemotherapy.

6. Procedures are to be repeated at the beginning of each cycle and can be assessed up to 2 days in advance of D1 for each cycle.
7. Three month interval begins from the end of completion of chemotherapy, and continues until 36 months after surgery (unless patient comes off study, per Section 6). These assessments can be +/- 14 days from planned date. Imaging assessments during follow-up can occur every 3-6 months, per investigator's standard practice. If subject has disease recurrence, follow-up will stop.
8. XRT treatment is reported once, at the completion of chemoXRT.

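### Section 7.2.1.2 gives two different 5-FU schedules for the Arm 2 chemotherapy-alone cycles (days 1 and 15 in the text, Day 1 only in the table), a twofold difference in planned dose

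*Combined protocol and SAP*

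**What the plan says.** Arm 2 (node positive) receives one cycle of chemotherapy, then five weeks of concurrent chemoradiation, then two more cycles of chemotherapy (Sections 7.2 and 7.3). In the chemotherapy-alone cycles the physician chooses capecitabine (7.2.1.1) or leucovorin with 5-FU (7.2.1.2).

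For the 5-FU option, the text of 7.2.1.2 reads "5-fluorouracil will be given on days 1 and 15 of a 28 day cycle according to the following", and then gives leucovorin 400 mg/m² and "5-fluorouracil will be dosed as 400 mg/m², IV bolus followed by a 1200 mg/m², IV infusion over 46 hours". The table beneath it gives the same doses, but lists Day 1 for leucovorin, Day 1 for the 5-FU bolus, and for the infusion "Continuous IV infusion Day 1-3 28-day cycle". Day 15 appears in no row.

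The checks around these cycles are tied to the start of a cycle:
- Section 6.3.1 (assessments): "While on chemotherapy alone, within 2 days before Day 1 treatment of each cycle".
- Section 7.4.4 (blood-count thresholds): "On Day 1 of each cycle (or, up to 2 days before Day 1), patients must meet the following criteria".
- Section 15.2, footnote 6 (schedule): "Procedures are to be repeated at the beginning of each cycle and can be assessed up to 2 days in advance of D1".

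Section 10.0 makes completion of the recommended therapy the primary endpoint and adds that, for chemoradiation to be feasible in node-positive patients, "a majority of patients must be able to receive this chemoradiation in its entirety".

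**The concern.** The text calls for two administrations per cycle and the table for one. Two patients can both be treated according to protocol and be planned for 5-FU doses that differ by a factor of two in these cycles. If the table is right, a site that follows the text gives double the intended dose. If the text is right, a site that follows the table gives half.

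There are two further consequences. First, if the text governs, the day 15 dose has no protocol-scheduled blood count or adverse event assessment and no numeric threshold for proceeding. Arm 1 FOLFOX, also given every 14 days, is written as a 14-day cycle and so is checked before every dose. Second, the trial exists to measure whether patients complete this sequence. What counts as all of the protocol therapy differs between the two readings.

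**Working it through.** The plan states no cumulative dose, so there is no figure to reproduce. The check is to set the two schedules side by side and multiply out.

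**Inputs**
- 5-FU per administration (7.2.1.2, text and table agree): 400 mg/m² bolus + 1,200 mg/m² infusion = 1,600 mg/m².
- Leucovorin per administration (7.2.1.2): 400 mg/m².
- Administrations per 28-day cycle: 2 by the text, 1 by the table.
- Chemotherapy-alone cycles (7.2, 7.3): 1 + 2 = 3.
- Concurrent phase (7.2.2), text and table in agreement: 45 Gy / 1.8 Gy = 25 fractions, with 200 mg/m² 5-FU on each radiation day.

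**Formula:** planned dose = administrations per cycle × dose per administration × cycles, with no dose modification.

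| Quantity | Text (days 1 and 15) | Table (Day 1) | Ratio |
|---|---|---|---|
| Administrations per cycle | 2 | 1 | 2.0 |
| 5-FU per cycle, mg/m² | 2 × 1,600 = 3,200 | 1 × 1,600 = 1,600 | 2.0 |
| Administrations, three cycles | 6 | 3 | 2.0 |
| 5-FU, three cycles, mg/m² | 6 × 1,600 = 9,600 | 3 × 1,600 = 4,800 | 2.0 |
| Leucovorin, three cycles, mg/m² | 6 × 400 = 2,400 | 3 × 400 = 1,200 | 2.0 |
| Concurrent 5-FU, mg/m² | 25 × 200 = 5,000 | 5,000 | 1.0 |
| Whole 5-FU course, mg/m² | 9,600 + 5,000 = 14,600 | 4,800 + 5,000 = 9,800 | 1.49 |

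**Sensitivity**
- If the 1,200 mg/m² infusion were read as a daily dose for two days, one administration would be 400 + 2,400 = 2,800 mg/m². The cycle totals would be 5,600 and 2,800 mg/m², still twofold.
- Section 7.3 allows a change of fluoropyrimidine after chemoradiation, so a patient may have one, two or three 5-FU cycles. The gap is then 1,600, 3,200 or 4,800 mg/m².

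**Does anything else settle it?**
- The schedule in Section 15.2 marks adjuvant chemotherapy once per 28-day cycle, without dosing days.
- The clause in Section 7.0 that defers to standard practice names infusion times, dose modifications, delays and supportive care. Planned dosing days are not among them. Section 7.4.7 covers only modifications for toxicity.
- The table is hard to read as one administration to be repeated. The weekday CAPEOX table in 7.1.1 lists all three blocks of capecitabine days, up to days 15-19, and FOLFOX is handled by a 14-day interval.

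**Effect on the endpoint.** A patient given 5-FU on Day 1 only in all three cycles has received 3 of 3 planned administrations by the table and 3 of 6 by the text.

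**Related cross-reference.** For treatment criteria during chemoradiation, Section 7.2.2.3 says "Criteria for proceeding with treatment and managing side effects will be as in 5.1.3". Item 3 of Section 5.1 is the surgical inclusion criterion. The parallel clause 7.2.1.3 points to Section 7.4, which is presumably what was meant.

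**The case against.** The two readings may not be equally likely. The sentence states the days outright, and the table has the same layout and day entries as the 14-day FOLFOX table in 7.1.2, so day 15 may simply have been lost when that table was adapted. This is a reasonable inference, but it remains an inference. The protocol has no rule that text outranks table, and a reader working from the table would not see day 15.

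The effect on the primary endpoint is conditional. Section 10.0 does not define completion by doses. If completion is scored by cycles started or finished, both schedules can give the same result. This stands: no change in the completion rate has been shown, and the missing definition is a separate matter. Any definition still has to refer to a planned regimen.

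The day 15 safety point has limits too. Section 13.6.1 collects adverse events throughout treatment, 7.2.1.3 refers these cycles to Section 7.4, and clinicians may well check counts before day 15 under standard practice. That is fair, but collecting events is not a check before dosing, and the numeric thresholds in 7.4.4 are written for Day 1.

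Finally, exposure is unknown and may be small. It is also true that Section 3.2 calls the components established; what it describes as experimental is giving chemoradiation after preoperative chemotherapy and surgery. Neither point removes the contradiction.

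**Conclusion.** The concern holds. Section 7.2.1.2 contradicts itself in its current wording, and nothing else in the document resolves it. In the chemotherapy-alone cycles the planned 5-FU and leucovorin doses differ twofold: 9,600 against 4,800 mg/m² of 5-FU over three cycles. Over a course with 5-FU throughout, the ratio is 1.49. These figures assume full doses and all cycles given.

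Only Arm 2 patients who receive 5-FU in these cycles are affected. The documents do not say how many that will be, so the range is 0 to 30 of the 30 planned. The capecitabine option and the concurrent phase are consistent and untouched.

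The correction is necessary because this is a cytotoxic order with two readings, and because it changes what counts as protocol therapy. It does not rest on a demonstrated bias in the primary analysis. The cross-reference error in 7.2.2.3 is real but minor.

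**What to change.** Have the investigators confirm the intended schedule, then make text and table agree.

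- **If the text governs:** change the table to Days 1 and 15 (infusion Days 1-3 and 15-17), and state whether the Day 1 checks in 6.3.1, 7.4.4 and footnote 6 of 15.2 also apply before day 15.
- **If the table governs:** delete day 15 from the text.
- **In either case:** score completion of the 5-FU cycles against that single schedule. This does not replace a definition of completion in Section 10.0.
- **Side correction:** in 7.2.2.3, replace the reference to 5.1.3 with Section 7.4. Because the 7.4.4 thresholds are written for Day 1 of a cycle, also state how they apply to the weekly laboratory tests during chemoradiation (6.3.2).

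The cost is a short amendment: one table or one sentence, plus one cross-reference with a line on the weekly thresholds. If the text governs, add a day 15 line in the assessment schedule and one check per 5-FU cycle. No extra patients are needed.
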